## 2.7 Effect modification, subgroup, and sensitivity analyses

A subgroup analysis will be performed for the primary endpoint using only patients who present with symptoms at baseline.

A statistical interaction term between treatment arm and the following baseline characteristics will be added to the Cox proportional hazards model to test for effect modification.

- 1) CT value < 30 from the baseline OP swab,
- 2) presence of antibodies as defined by presence of IgG antibodies to SARS-CoV-2 Spike Receptor Binding Domain (RBD) at baseline, as measured by ELISA. Samples are considered seropositive against RBD if their absorbance value was greater than the mean of plus four standard deviation (SD) of all negative controls (n=130),
- 3) number of risk factors or predictors for severe disease present at baseline (temp 99.5+, cough, or shortness of breath present at randomization [symptoms count as a single risk factor], age  $\geq$  60, male sex, Black race, Hispanic ethnicity, BMI  $\geq$  30, and lab values of baseline lymphocyte counts <1000 and baseline ALT  $\geq$  94),
- 4) age  $\geq$  50,
- 5) sex

A Wald test performed at the alpha = 0.05 level of significance will be used to test whether the effect modification is statistically significant. The sensitivity and effect modification analyses will be performed in other key endpoints as well.

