## 1 STUDY DETAILS

### 1.1 Study design

This phase 2 randomized, single-blind study intends to evaluate the efficacy of a single dose of peginterferon lambda-1a in outpatients with mild COVID-19 compared with placebo in reducing the duration of shedding of SARS-CoV-2 virus.

One hundred and twenty (60 per arm) enrolled patients will be randomized in a 1:1 fashion. Thus, there will be two arms: (1) the control arm, comprised of placebo in addition to standard supportive care and (2) the treatment arm, comprised of a single dose of peginterferon lambda-1a in addition to standard supportive care. An interim analysis for safety and overwhelming efficacy will be performed once 50% of patients have 24 hours of follow-up complete.

The primary analysis is based on intent-to-treat principles in that all patients who are randomized to study arm are included in the analysis, where cessation of shedding is assessed according to randomized study arm. The secondary analysis of adverse events (AE) are assessed according to dose received.

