### 4.2 Determination of sample size

We assume that the mean duration of virologic shedding in individuals receiving standard of care is 14 days, with a standard deviation of 4 days.

Assuming 1:1 randomization and the use of a two-sided log rank test at the alpha=0.04999 level of significance for the final analysis, 79 events will provide 80% power to detect a hazard ratio of 2.03. This leaves alpha=0.00001 to check for overwhelming efficacy after 50% of participants have completed 24 hours of follow-up. Assuming the control and treatment arm median cessation of shedding is 14 and 7 days, respectively, a two-month accrual period, a two-week follow-up period after randomization of the last patient, and a drop out of 10% in the control arm, it is estimated that the total sample size required to achieve 79 events is 120 (60 patients in each arm).

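### The effect-modification test for baseline Ct uses only an unexplained cut at 30, which lowers the power of an already weak test if modification is gradual

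*SAP*

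**What the plan says.** SAP 2.7 lists five baseline modifiers of the treatment effect. It states: "A statistical interaction term between treatment arm and the following baseline characteristics will be added to the Cox proportional hazards model". The first modifier is "CT value < 30 from the baseline OP swab". On inference it says: "A Wald test performed at the alpha = 0.05 level of significance will be used". It also extends these analyses to other key endpoints.

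The documents give no reason for the value 30, plan no interaction with Ct on its full scale, and state no power for any interaction. SAP 2.7 mentions only the interaction term; it does not say that the modifier's main effect enters the model.

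Elsewhere the SAP keeps the same measurement quantitative. SAP 2.4 models log viral load over time and computes an AUC from log10 load, with day 0 included. SAP 2.5 relates Ct values to symptoms. SAP 2.4 also sets results beyond the detection limit to Ct 42 when deriving viral load. The primary model (SAP 2.3) adjusts for age and sex only.

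**The concern.** A cut at 30 treats patients at Ct 29 and 31 as different and patients at 16 and 29 as alike. If the benefit of an antiviral changes gradually with viral load, the variation within each group carries information that the test does not use. The age cut at 50 in the same list at least matches a randomization stratum (SAP 1.5); the Ct cut has no such basis in the documents.

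At stake is one secondary question: whether the trial can say anything about benefit by baseline viral load. Interaction tests in a trial sized for a main effect have little power, so an avoidable loss is worth removing when that costs only wording.

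**Working it through.** **Inputs from the documents.** 120 patients, 60 per arm (SAP 1.1). For the main effect, SAP 4.2 says "79 events will provide 80% power to detect a hazard ratio of 2.03", using a "two-sided log rank test at the alpha=0.04999 level of significance for the final analysis". The interaction test is a Wald test at 0.05 (SAP 2.7), taken here as two-sided.

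**Inputs not in the documents.** The mean and SD of baseline Ct, the share below 30, the share undetectable, and the shape of any modification. These are assumed and varied below.

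**The plan's own figure.** Schoenfeld's formula gives D = 4(1.960 + 0.842)²/(ln 2.03)² = 4 × 7.85/0.501 ≈ 63 events, and Freedman's gives 68. The stated 79 is not reproduced; at 79 events, power for 2.03 is about 88% by Schoenfeld. That is a separate matter. I use 79 events because it is the planned number, and show 63 and 100 alongside.

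**Power of the interaction with a binary modifier.** With share p below 30 and D events, SE = √[4/(Dp) + 4/(D(1−p))].

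- D = 79, p = 0.5: SE = √(8/79 + 8/79) = 0.45. For a ratio of hazard ratios of 2.03, as large as the planned main effect, z = 0.708/0.45 = 1.57 and power = Φ(1.57 − 1.96) ≈ 35%. For a ratio of 1.5, power is about 15%. The ratio detectable with 80% power is exp(2.80 × 0.45) ≈ 3.5.
- D = 79, p = 0.84: SE = 0.61, power for 2.03 about 21%, detectable ratio about 5.6.
- D = 100, p = 0.5: power for 2.03 about 43%. D = 63, p = 0.5: about 29%.

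**Information lost by the cut.** For a normal covariate with a linear effect, cut k SD from its mean, the share of information kept is φ(k)²/[p(1−p)], with p = Φ(k).

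| Assumption | Kept | Lost |
|---|---|---|
| Normal, linear, k = 0 | 0.637 | 36% |
| Normal, linear, k = 0.5 | 0.581 | 42% |
| Normal, linear, k = 1 | 0.439 | 56% |
| Normal, linear, k = 1.25 | 0.353 | 65% |
| Normal, linear, k = 1.5 | 0.269 | 73% |
| Normal, linear, k = 2 | 0.131 | 87% |
| Uniform Ct, linear, cut at median | 0.75 | 25% |
| Effect truly steps at 30 | 1 | none |

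**Where 30 might lie.** Protocol 2.1.1 cites a median oropharyngeal load of 10⁶ copies in another cohort. With the SAP 2.4 constants, and the sign taken so that load falls as Ct rises, Ct 30 is (42 − 30) × 0.23 = 2.76 log10. With an assumed SD of 2 to 2.5 log10, the cut lies (6 − 2.76)/2 = 1.6 to (6 − 2.76)/2.5 = 1.3 SD from the centre, and the loss is about 66–77%. This illustrates the sensitivity and is not an estimate for this trial.

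**Effect on power.** For a continuous modifier, the SE per SD is 2/√D = 2/√79 = 0.225. For a cut, z is multiplied by the square root of the share kept.

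| Assumed interaction (log HR per SD), 79 events | Continuous | Cut at mean | Cut at 1 SD |
|---|---|---|---|
| 0.35 (z = 1.56) | 34% | 24% | 18% |
| 0.50 (z = 2.22) | 60% | 43% | 31% |

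A Cox simulation at 0.50 per SD, with 120 patients, 28-day censoring and about 97 events, gave 66%, 46% and 30%. Even with continuous Ct, 80% power at 79 events needs 2.80 × 0.225 ≈ 0.63 per SD, a ratio of hazard ratios of about 1.9 per SD.

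**The case against.** The strongest reply is that no particular loss can be assigned to this trial. A reader might infer that the cut discards 36–56% of the information in Ct. The documents do not support that: the range needs a normal Ct, a linear effect and a cut within 1 SD of the mean, and they give none of the three.

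Normality is also doubtful. Eligibility (protocol 6.2) requires a recent positive diagnostic assay, not a positive baseline oropharyngeal swab, and admits asymptomatic patients. Undetectable baseline swabs, set to Ct 42, may therefore pile up. With Ct mean 24, 28 or 32, SD 4 or 6, and 0–30% of patients at 42 (all assumed), the loss under a linear effect runs from about 16% to 73%.

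Nor is a straight line always better. If the effect changes smoothly but mainly around Ct 30 (assumed logistic, scale 1.5 Ct), the cut keeps 71–94% of the information and a linear term 59–94% over the same grid. Values at 42 also give a linear term high leverage. Two subgroup hazard ratios cannot check linearity, since two points always fit a line.

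Finally, the cut is pre-specified and therefore not data-driven, and this is one of five interaction tests outside the primary analysis.

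All of this stands. It limits the size of the claim and shapes the fix. It supplies neither a reason for 30 nor a reason to leave out the full-scale test.

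**Conclusion.** The point holds as a small, inexpensive improvement. The effect-modification test for Ct rests on a single unexplained cut of a measurement that the SAP otherwise keeps quantitative. Under roughly linear modification the cut lowers power, for example from 34% to 24% at 0.35 per SD with 79 events and a cut at the mean of a normal Ct. The loss of information could be nil if the effect steps at 30, and above 65% if a normal Ct is cut more than 1.25 SD out. Without the baseline distribution it cannot be narrowed.

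Two further inferences should be resisted. Continuous Ct would not make this an adequately powered test; it remains exploratory either way. And the primary result is not affected, because baseline Ct does not enter the SAP 2.3 model.

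**What to change.** Amend SAP 2.7, before unblinding, as follows:

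- Base the Wald interaction test for baseline viral load on continuous baseline Ct (or log10 viral load), and state that its main effect is in the model.
- Check linearity with a restricted spline or at least three Ct groups.
- For undetectable baseline swabs, apply the SAP's Ct 42 substitution and either add an indicator for them or repeat the analysis without them.
- Keep the Ct 30 split only to display subgroup hazard ratios, and give the reason for 30.
- Use the same form where the analysis is carried to other endpoints, and describe the result as exploratory, with a confidence interval.

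The cost is a few lines of SAP text. No new data are needed: protocol 9.3 already provides quantitative results from the study swabs. The downside is a linearity assumption and leverage from values placed at Ct 42, which the second and third items address.

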## 3 HANDLING OF MISSING AND CENSORED DATA

All efforts will be made to minimize instances of missing data. However, we expect some missing data will occur. Our analyses will assume data are missing at random. For the primary endpoint of time to shedding cessation, any participant who drops out prior to having two consecutive negative tests will be censored at their last positive test. Participants who have no post-randomization test results available or a single test result that is negative will be censored at day 1. Similarly, participants will be right censored for the time to symptom resolution or progression at the time when their last symptom questionnaire is completed. Participants who are asymptomatic at screening and never report symptoms thereafter will be considered to have met symptom resolution at study Day 1. For other missing data, we will use multiple imputation-based analyses. This approach will be applied to any analysis involving endpoints or key

variables where any missing data occurs in order to adhere to the ITT principle. Sensitivity to assumptions regarding missingness will be addressed through sensitivity analyses.

If more than 5% of participants do not have the time of shedding cessation observed (i.e. they are right-censored), we will perform a sensitivity analysis to evaluate the robustness of our findings to missing data assumptions. In the sensitivity analysis, among those missing timing of shedding cessation, we will assume varying proportions (e.g. 25%, 50%) of participants in each arm who would have ceased shedding by Day 28. The proportions will differ by arm so we can evaluate whether our findings stand if it were true that people who dropped out stopped shedding earlier in the placebo arm vs the active arm.

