9 SUBJECT MANAGEMENT

9.1 Subject Follow-up

9.1.1. In home assessments.

Participants will complete an at-home symptom questionnaire by REDcap on each day of follow-up through day 28, including in-home assessments of temperature and O2 saturation. These assessments will be reviewed daily by a clinical research coordinator, and patients will be telephoned by a physician if they report an elevated temperature, diminished O2 sat (<94%), or signs/symptoms of respiratory or cardiopulmonary distress (e.g. shortness of breath, dyspnea on exertion). On each day through day 28, patients will also be instructed to collect an anterior nare swab in a pre-labeled container and to store these specimens in a refrigerator at 2°C to 8°C, and to bring these in to their next scheduled appointment. Prior to the optional follow up visits at months 4, 7 and 10, participants will complete an at-home symptom questionnaire and will be asked to collect a stool specimen to bring to their next scheduled appointment.

9.1.2. Follow-up in-clinic assessments.

[figure not shown]
Participants will be seen at follow-up visits at Day 1±1, 3±1, 5±1, 7±1, 10±1, 14±1, 21±1, and 28±1. At each visit, a subjective medical history will be performed, including assessments for use of any concomitant medications. Vital signs will be obtained (temperature, blood pressure, pulse rate per minute, breath rate per minute and oxygen saturation), and oropharyngeal and anterior nare swabs will be collected. Participants will also submit at-home collected anterior nare swab specimens for evaluation. Clinical laboratory measurements will be performed at days 5±1 and 14±1 to assess for safety, with additional clinical laboratory assessments performed as needed for clinical follow-up and/or patient management. Additionally, ~25 mL peripheral blood will be collected from study participants at enrollment and at Days 5±1, 14±1, and 28±1 for processing and cryopreservation into a specimen biobank. Safety and tolerability of Lambda will be assessed by adverse event (AE) monitoring, vital signs assessment and clinical laboratory tests. Patients will reach the end of study at day 28±1 of follow-up. Optional long-term follow up visits will be scheduled 4, 7, and 10 months post-enrollment. The window of ±3 weeks is allowed for these long term follow up visits.

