### 1.3 Secondary endpoints

Secondary endpoints include the following:

- Time until resolution of all symptoms;
- SARS-CoV-2 viral load over time in oropharyngeal tests;
- SARS-CoV-2 viral load area under the curve in oropharyngeal tests through Day 14;
- Number of emergency department visits or hospitalizations within 28 days of treatment.

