### 1.4 Exploratory endpoints

Exploratory endpoints include the following:

- Time until sustained symptom resolution;
- Time until resolution of respiratory symptoms (cough, sore throat, runny nose, chest pain, and shortness of breath);

- Time until resolution of systemic and respiratory symptoms (headache, fever/chills, muscle/joint pain, fatigue and respiratory symptoms described above);
- Time until disease progression;
- SARS-CoV-2 infection-free by negative RT PCR testing results from nasal swabs on Days 5, 7, 10, and 14;
- SARS-CoV-2 infection-free by negative RT PCR testing results from oropharyngeal swabs on Days 5, 7, 10, and 14;
- SARS-CoV-2 viral load over time in nasal tests;
- SARS-CoV-2 viral load area under the curve in nasal tests through Day 14;
- Seroconversion by Day 28 (presence of IgG antibodies to SARS-CoV-2 Spike Receptor Binding Domain, as measured by ELISA);
- Cellular immune responses;
- Host genetics.

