Area under the curve (AUC) will be defined by a single participant's logarithmic base 10 viral load from oropharyngeal tests collected on days 0, 1, 3, 5, 7, 10, and 14. AUC will be calculated by the trapezoidal rule, using exact times of collection of each OP swab. Multiple imputation using chained equations will be used to impute missing viral load data prior to AUC calculation. Five data sets will be imputed, and imputed values will be calculated using non-missing viral load on each of the 7 sample collection days, treatment arm, age, sex, and whether or not a participant was hospitalized. A pooled linear regression model will be fit to log-transformed AUC as a function of treatment, age, and sex using the 5 imputed data sets. Difference in AUC by treatment arm and corresponding 95% confidence intervals will be reported using Rubin's Rules. The difference in AUC by treatment arm will also be done after refitting the model without participants who were hospitalized to assess sensitivity of results.

The incidence of hospitalizations and emergency department visits will be estimated for each arm, with 95% confidence intervals.

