## 2.5 Exploratory efficacy analyses

An alternative definition of the secondary endpoint of symptom resolution will be considered in an exploratory analysis. We will evaluate time to sustained symptom resolution, defined as time from randomization until the first day in which no symptoms are reported and are not reported for the duration of the study. The analysis of time to sustained symptom resolution will follow the methods described for the secondary endpoint evaluation symptom resolution in the previous section. Time to symptom resolution based on symptom subsets (i.e. respiratory, systemic) will be similarly analyzed, additionally excluding participants who did not report symptoms from the specified subset at screening.

Time to disease progression will be defined as the time from randomization until the first day of a two point or more increase in either cough or shortness of breath persisting for at least 48 hours or an increase to a score of 4 or 5, or first day of admission to the emergency department, hospitalization, or death. Analysis and reporting of results will be done following methods detailed for time to symptom resolution.

Freedom from SARS-CoV-2 infection by oropharyngeal and nasal swabs at Day 5, 7, 10, and 14 will be modeled using a multivariable logistic regression model adjusted for age and sex. The odds ratio will be presented along with its 95% confidence interval.

Similar approaches to those used for evaluating SARS-CoV-2 viral load in oropharyngeal tests over time and AUC will be used to evaluate viral load in nasal tests.

Correlation between virology and symptomology will be characterized by evaluating the relationship between CT values obtained from the oropharyngeal tests and each symptom through two main approaches. For symptoms graded on an ordinal scale, we will calculate a Spearman correlation and assess significance with a Z-test. For variables that capture presence of a symptom, differences in the median CT values by presence or absence of the symptom will be presented and assessed via a Wilcoxon rank sum test.

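### The exploratory progression endpoint includes ED admission, hospitalization and death, yet SAP section 3 censors it at the last symptom questionnaire; the two kinds of component need separate dates

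*SAP*

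**What the plan says.** SAP section 1.4 lists "Time until disease progression" among the exploratory endpoints. SAP section 2.5 makes it a composite. One part is symptom worsening: the "first day of a two point or more increase in either cough or shortness of breath persisting for at least 48 hours", or a rise to a score of 4 or 5. The other part is clinical: "or first day of admission to the emergency department, hospitalization, or death".

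On method, section 2.5 says: "Analysis and reporting of results will be done following methods detailed for time to symptom resolution". That means Kaplan-Meier curves and a Cox model adjusted for age and sex.

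SAP section 3 gives symptom resolution and progression the same censoring rule: "participants will be right censored for the time to symptom resolution or progression at the time when their last symptom questionnaire is completed". The form is a daily home diary. Protocol section 9.1.1 says: "Participants will complete an at-home symptom questionnaire by REDcap on each day of follow-up through day 28".

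ED visits and hospitalizations also have their own secondary endpoint (SAP section 1.3): "Number of emergency department visits or hospitalizations within 28 days of treatment". Section 2.4 gives its analysis: "The incidence of hospitalizations and emergency department visits will be estimated for each arm, with 95% confidence intervals". Neither document says whether a documented admission or death after the last questionnaire still counts as progression, and neither gives a different censoring date for those components.

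**The concern.** The questionnaire is the only daily source for the symptom scores, so it is a sensible limit for that part of the composite. It is not the source for ED admission, hospitalization or death. Using its last completion date for the whole composite ties the observation of the most serious events to a form that a very ill participant may stop completing.

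Two things are at stake. First, the trial could report an admission in its secondary endpoint and treat the same person as progression-free in the progression curve. Secondly, if people stop the diary because they are deteriorating, the censoring is informative, which sits badly with the missing-at-random assumption in SAP section 3. Death adds some weight, because it is not part of the secondary ED/hospitalization endpoint and progression is the only listed efficacy endpoint that includes it.

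**Working it through.** The documents give no event rate, power or sample size for progression, so there is no stated figure to reproduce. The check is of the rule itself.

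**Inputs.** T is the day of first progression (SAP 2.5). C is the day of the last completed questionnaire (SAP 3). N = 120, 60 per arm (SAP 1.1).

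**Step 1: literal reading.** Observed time is min(T, C), and the event is counted only if T ≤ C.
- Last form on Day 6, hospitalized on Day 7, no form afterwards: T = 7, C = 6, min(T, C) = 6. The participant is censored without an event.
- Same history, but the participant completes any form on Day 7 or later: C ≥ 7, so the event on Day 7 is counted.

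A missed form on the day of deterioration therefore does not lose the event. The diary must stop for good before the event day.

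**Step 2: the symptom component.** If the participant had already reported a score of 4 or 5, or a two-point rise lasting at least 48 hours, T is that earlier day and nothing is lost. If the diary stops at admission less than 48 hours into a two-point rise, with no score of 4 or 5, it may be unable to show a qualifying worsening. Both conditions are needed for a loss: no form from the event day onward, and no earlier symptom progression.

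**Step 3: charitable reading.** Suppose the rule applies only to participants with no event. Take two people whose last form is on Day 6. One is hospitalized later: that event is counted on its own date, so this person stays at risk beyond Day 6. The other has no event and leaves the risk set on Day 6, even if known to be out of hospital and alive later. Staying in the risk set then depends on the outcome. If d serious events occur on a later day, n participants are truly at risk, and m of them are event-free people already removed, the estimated step is d/(n − m) instead of d/n. This is too large whenever m > 0. The documents do not give m.

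**Step 4: hypothetical counts under the literal reading.** Let p be the share of participants whose first progression is a serious event, and g the share of those whose diary stopped for good beforehand. Events = 120 × p; events lost = 120 × p × g. Neither p nor g is in the documents; the values below are assumptions.

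| p | Events | Lost, g = 0 | Lost, g = 25% | Lost, g = 50% | Lost, g = 75% |
|---|---|---|---|---|---|
| 5% | 6 | 0 | 1.5 | 3 | 4.5 |
| 10% | 12 | 0 | 3 | 6 | 9 |

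If true rates were equal but g were 25% in one arm and 50% in the other, the ratio of counted serious events would be (1 − 0.50)/(1 − 0.25) = 0.67 instead of 1. Nothing in the documents indicates that g would differ by arm.

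**The case against.** The strongest reply is that the literal reading is not the natural one. The sentence sits in a section on missing and censored data, is introduced as analogous to the rule for participants who drop out before clearing virus, and SAP section 1.2 censors only patients who do not reach the primary endpoint. An admission with a known date is neither missing nor censored. This has force, and the authors may well have meant event-free participants only. But the shedding rule states that condition and the progression rule does not. Step 3 also shows that the charitable reading leaves a mismatch of its own.

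A reader might go further and infer that one missed form is enough to lose an event, that most serious progressions would disappear, or that the trial would lose sight of them. The documents support none of these. Censoring is at the last form, not the first missed one. Forms are reviewed daily by a coordinator, with a physician call for reported low saturation or respiratory symptoms (Protocol 9.1.1). ED visits and hospitalizations stay in the secondary endpoint. Deaths and inpatient hospitalizations are serious adverse events (Protocol 10.1.3) and are tabulated by arm (SAP 2.6).

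It is also fair to say that status to Day 28 will not be known for everyone. Under the protocol's section on withdrawal of subjects, no further procedures are possible for those who cannot be located or who withdraw consent. That stands, and the censoring date has to allow for it.

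**Conclusion.** The point holds as a defect in the censoring rule for one exploratory endpoint. On the literal reading, a documented serious event is lost if the participant completes no questionnaire from the event day onward and had no earlier qualifying symptom worsening. On the charitable reading, no documented event is lost, but events and time at risk come from different sources and progression risk is somewhat overstated. The errors run in opposite directions, and the text does not say which reading applies.

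The size cannot be derived from the documents. The range in Step 4, from 0 to 9 events lost, follows entirely from assumed values and is not an estimate; a reader should not take its upper end as the expected loss. Nor do the documents show a bias between arms. The primary endpoint, the secondary ED/hospitalization endpoint and the safety tables are unaffected. The general commitment in SAP section 3 to sensitivity analyses does not resolve this, because only the one for shedding cessation is specified.

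**What to change.** Split the rule for progression in SAP section 3:

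1. A documented ED admission, hospitalization or death within 28 days counts as progression on its own date, whatever the questionnaire status, unless a qualifying symptom worsening came first.
2. Participants without an event are censored at the last date on which their ED, hospital and vital status is known: at most Day 28, or the withdrawal or last-contact date if earlier.
3. The last questionnaire limits only the symptom-score component.
4. A sensitivity analysis censors everyone at the last questionnaire.

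The rule for symptom resolution can stay as it is. The cost is a few sentences and one extra model run. No new data collection is needed, since ED visits and hospitalizations to Day 28 are already a secondary endpoint and deaths are captured as serious adverse events. The downside, which the SAP should state, is that symptom worsening is unobserved between the last questionnaire and last contact, so event-free participants are treated as free of it over that interval. Item 4 shows whether this matters.
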